# 2.7.2 Effectiveness

At the time of the first interim analysis (Month 72), summaries of the incidence of HPV 6, 11, 16, 18, 31, 33, 45, 52, and 58 related persistent infection for a duration of  $\geq 6$  months (within  $\pm 1$  month windows) and cervical, vulvar, vaginal, perineal, perinal, and penile intraepithelial preinvasive and invasive disease, and external genital lesions will be provided, separately for males and females. Similar summaries of the incidence rates of HPV 6, 11, 16, 18, 31, 33, 45, 52, and 58-related persistent infection for a duration of  $\geq 6$  months (within  $\pm 1$  month windows) and disease will be provided to include follow-up data through the second interim analysis at Month 96 and at the end of the study at Month 126.

All subjects will contribute to the effectiveness summaries. Summaries will be provided by gender and age group (based on age at enrollment). The primary analysis group will be those who have received 3 doses of 9-valent HPV L1 VLP vaccine within one year. Subjects will be considered breakthrough cases related to a given HPV type provided they were negative to the respective HPV type by serology prior to vaccination and were sexually naïve through the 3rd dose of 9-valent HPV L1 VLP vaccine. Sexual naïveté, an inclusion criterion for the base study, is being used as a way to limit analysis of the prophylactic effect of the vaccine to subjects who were not infected prior to completion of the vaccination series. There are no PCR data from Protocol V503-002 subjects until subjects reach their 16th birthday. Therefore, the only data available to assess possible prior infection are pre-vaccination serum anti-HPV levels and sexual history. Cases in subjects with evidence of HPV exposure or infection prior to vaccination (i.e., seropositivity to the relevant HPV type(s) pre-vaccination or sexual activity prior to completion of the vaccination series) or in subjects who did not receive 3 doses of 9valent HPV L1 VLP vaccine within one year will not be considered breakthrough cases (vaccine failures). Such cases will be summarized separately.

20

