#### **3.5.4.3 Effectiveness Analysis Populations**

Assessment of effectiveness will be conducted on two analysis populations: the perprotocol effectiveness (PPE) and the full analysis set (FAS) populations. The primary analysis will be conducted on the PPE population. The two analysis populations differ as described below with regard to compliance to vaccination regimen and potential HPV infection status at the time of vaccination of 9-valent HPV L1 VLP vaccine.

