#### Per-Protocol Effectiveness (PPE)

The PPE analysis population is HPV type-specific. In analyses of endpoints related to a specific HPV type (e.g., HPV 16-related endpoints) the PPE population-eligible subjects include those who:

- (1) received 3 doses of 9-valent HPV L1 VLP vaccine within 1 year; AND
- (2) were seronegative by cLIA to the specific HPV type at the time of injection of dose 1 of 9-valent HPV L1 VLP vaccine (seronegative to both types 6 and 11 in analysis of HPV 6-related, and HPV 11-related endpoints); AND
- (3) Have no other protocol violations that could interfere with the evaluation of the effectiveness of the study vaccine. Specifically, at base study Day 1, satisfied inclusion criterion 5 (i.e., " Subject must not yet have had coitarche and does not plan on becoming sexually active during the Day 1 through Month 7 period.") specified in Section 2.2 of the protocol of the base study (i.e., Protocol V503-002-00).

Inclusion criterion 5, at base study, was intended to capture subjects who had not yet been infected with HPV through sexual intercourse and were therefore likely to be HPV-naïve during the period of vaccination with 9-valent HPV L1 VLP vaccine. The seronegativity condition is another criterion intended to capture subjects who were still HPV-naïve during the period of vaccination of 9-valent HPV L1 VLP vaccine

Note that a subject can be both PPE population-eligible for analyses of endpoints related to one HPV type (e.g., HPV 16-related endpoints) and PPE population-ineligible for analyses of endpoints related to another HPV type (e.g., HPV 18-related endpoints).

In analyses of endpoints related to any vaccine HPV type (e.g., HPV 6/11/16/18/31/33/45/52/58-related endpoints), the PPE population-eligible subjects include those who are PPE population-eligible for *any of* the HPV types 6, 11, 16, 18, 31, 33, 45, 52, or 58.

Only PPE population-eligible subjects who are at least 16 years of age and have at least one follow-up visit with PCR data will contribute to the PPE analyses.

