#### **3.5.5.3 Statistical Methods for Effectiveness Analyses**

Subjects who meet the criteria to be considered cases of vaccine type HPV-related persistent infection and/or disease, but who have evidence of HPV exposure or infection (i.e., seropositivity to the respective HPV type(s) pre-vaccination or evidence of sexual activity prior to the completion of their vaccination series), or who do not complete their three doses of 9-valent HPV L1 VLP vaccine within one year, will not be considered breakthrough cases (i.e., vaccine failures). Such cases will be summarized separately in a manner similar to breakthrough cases, with all relevant factors such as baseline demographics and immunogenicity profiles over time characterized; however, these cases will not be included in the primary summary of effectiveness endpoints.

78

At the time of the interim analysis (Month 72), summaries of the incidence of HPV 6, 11, 16, 18-related persistent infection for a duration of  $\geq 6$  months (within  $\pm 1$  month windows) and cervical, vulvar, vaginal, perineal, perinanal, and penile intraepithelial preinvasive and invasive disease, and external genital lesions will be provided, separately for males and females. Similar summaries of the incidence rates of HPV 6, 11, 16, 18, 31, 33, 45, 52, and 58-related persistent infection for a duration of  $\geq 6$  months (within  $\pm 1$  month windows) and disease will be provided to include follow-up data through Month 96 and Month 126.

The confidence intervals around the point estimate of the incidence rates per 100 personyears are exact Poisson distribution-based nominal 95% confidence intervals.

Summaries will be provided by gender. At each analysis time point, the cumulative incidence rate for effectiveness endpoints will be computed, along with the associated 95% confidence interval. In addition, exploratory analyses will be conducted to characterize subjects who become cases of persistent infection or disease endpoints in the long-term effectiveness follow-up period. Baseline demographic characteristics, prevaccination anti-HPV serology status, and post-vaccination immunogenicity profiles will be considered. Time-to-event plots will also be provided by gender if >5 cases are observed in the respective group(s).

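### The breakthrough-case rule (2.7.2, 3.5.5.3) and the per-protocol effectiveness population (3.5.4.3) do not match, so some cases, notably HPV 6/11 serology-discordant ones, are classified differently by each

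*Combined protocol and SAP*

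**What the plan says.** **Population.** Section 3.5.4.3 names the primary set: "The primary analysis will be conducted on the PPE population". PPE eligibility is decided type by type. Condition (1) is three doses inside a year. Condition (2) is Day 1 seronegativity by cLIA to the type, with an explicit pairing: "seronegative to both types 6 and 11 in analysis of HPV 6-related, and HPV 11-related endpoints". Condition (3) reads "Have no other protocol violations that could interfere with the evaluation of the effectiveness of the study vaccine" and then names one requirement, that base-study inclusion criterion 5 (no coitarche, and no plan to become sexually active through Month 7) was met at Day 1. For endpoints covering any vaccine type, eligibility for any one of the nine types is enough.

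**Case rule.** Section 2.7.2 calls a case a breakthrough for a type if subjects meet two conditions: "they were negative to the respective HPV type by serology prior to vaccination", and sexually naive through dose 3. Section 3.5.5.3 states the reverse. A case is not a breakthrough if there is "evidence of HPV exposure or infection (i.e., seropositivity to the respective HPV type(s) pre-vaccination", or sexual activity before the series was complete, or failure to complete three doses within a year. Such cases are summarized separately, and "these cases will not be included in the primary summary of effectiveness endpoints".

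The FAS (3.5.4.3) is not type-specific and has no serology condition.

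**The concern.** The primary incidence rate needs a numerator and a denominator chosen by the same rule. Here the PPE definition fixes who contributes person-time, while a separately worded rule decides which cases are vaccine failures and which go to the side table. If the two are not complements, some cases fall between the tables, and some person-time stays in after its cases have been taken out.

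The count of vaccine failures is a main output of the two co-secondary effectiveness objectives. The plan allows for very low counts, since time-to-event plots are drawn only when more than 5 cases are seen. Section 3.5 says no separate SAP will be issued, so this text is the governing rule, and Section 3.5.1 says the extension is not blinded. Two analysts, one starting from 3.5.4.3 and the other from 3.5.5.3, could report different numbers of vaccine failures.

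**Working it through.** The plan gives no figure on this point, so there is none to reproduce. The check applies both written rules to the same subjects.

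**(a) HPV 6/11 serology.** Cross the case type with Day 1 serostatus, all other conditions being met:

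| Case type | Sero 6 | Sero 11 | Breakthrough (2.7.2, 3.5.5.3) | PPE-eligible for the type (3.5.4.3) |
|---|---|---|---|---|
| 6 | − | − | yes | yes |
| 6 | − | + | **yes** | **no** |
| 6 | + | − | no | no |
| 6 | + | + | no | no |
| 11 | − | − | yes | yes |
| 11 | − | + | no | no |
| 11 | + | − | **yes** | **no** |
| 11 | + | + | no | no |

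The rules agree in 6 of 8 combinations and conflict in 2. In those two, the case is a vaccine failure by label, is outside the type-specific PPE analysis, and meets none of the 3.5.5.3 reasons for the separate summary. Adding the 6/11 pairing to the breakthrough rule brings the serology conflicts to 0 of 8.

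**(b) Composite.** A subject seropositive only to HPV 11 is ineligible for types 6 and 11 but eligible for the other seven, so her person-time is in the nine-type PPE denominator. Whether her HPV 6 case then counts is not stated. Read literally, the breakthrough rule would count it.

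**(c) Sexual activity.** The breakthrough rule looks through dose 3; PPE condition (3) applies criterion 5 at Day 1. A subject who became active between Day 1 and dose 3 can keep her person-time in the PPE while her case is removed. If such subjects hold a fraction f of PPE person-time and have the same case rate as the rest, the reported rate is (1 − f) times the rate with numerator and denominator aligned. The documents do not give f.

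**(d) Other violations.** These remove a subject from the PPE under condition (3) but are not among the reasons in 3.5.5.3, so the case has no assigned table.

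**Weight of one case.** Section 3.5.5.3 specifies exact Poisson intervals. For k cases in T person-years, the limits per 100 are 100·χ²(0.025; 2k)/(2T), taken as 0 when k = 0, and 100·χ²(0.975; 2k+2)/(2T). T is assumed, because the documents give none:

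| T (assumed) | 0 cases, rate (95% CI) | 1 case, rate (95% CI) |
|---|---|---|
| 1000 | 0 (0 to 0.369) | 0.100 (0.003 to 0.557) |
| 3000 | 0 (0 to 0.123) | 0.033 (0.001 to 0.186) |
| 6000 | 0 (0 to 0.061) | 0.017 (0.0004 to 0.093) |

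**How many such cases.** Day 1 seroprevalence is not given. If 1% to 5% of the 2552 three-dose subjects (Section 1.5) were seropositive to exactly one of HPV 6 and 11, that is 26 to 128 subjects. Months 42 to 126 are 84/12 = 7 years at most. At an illustrative 0.10 cases per 100 person-years for all vaccine types, the expected number is 26 × 7 × 0.001 = 0.18 to 128 × 7 × 0.001 = 0.90, before dropout. It is lower again for HPV 6 and 11 alone.

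**The case against.** The strongest reply is that nothing important is undefined. Section 2.7 presents itself as a summary and defers to 3.5. Section 3.5.4.3 fixes the primary population and states the 6/11 pairing. The plural in "seropositivity to the respective HPV type(s) pre-vaccination" can be read to fit that pairing. On that view only a label and a side table remain open, for very few subjects, in a study that tests no hypothesis.

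Much of this stands. Membership of the HPV 6- and HPV 11-specific PPE analyses is clear, and the numbers are likely to be small: subjects were enrolled as sexually naive at 9 to 15 years, and a conflict needs discordant serology plus a case of the other type. The plural does not settle the matter, though. It reads as naturally for a case involving more than one type, nothing in 3.5.5.3 mentions the pairing, and 2.7.2 uses the singular when it defines a breakthrough. The sexual-activity difference does not depend on that reading.

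The other-violations gap is also narrow. The only violation that 3.5.4.3 names is criterion 5, and sexual activity is already listed in 3.5.5.3, so only unspecified violations are affected.

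A reader might infer more than the text supports:

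- **That a discordant case disappears from reporting.** It does not: it stays in the FAS, and 3.5.5.3 plans an exploratory description of all cases that takes in pre-vaccination serology.
- **That the discordant subject contributes no PPE person-time.** That is true only of the HPV 6- and 11-specific analyses, not of the composite.
- **That the mismatch falls on the most likely disease component.** Section 3.1.1.2 gives the share of anogenital warts due to HPV 6 and 11 (over 90%), not the frequency of warts relative to other endpoints.

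**Conclusion.** The inconsistency is real. Two stated rules classify the same case differently in 2 of the 8 HPV 6/11 serology combinations. They also differ on the sexual-activity period and on other protocol violations, and the composite has no rule for a case of a type for which the subject is PPE-ineligible.

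The numerical effect is probably small and cannot be computed from the documents. The 1% to 5% discordance, the 1000 to 6000 person-years and the 0.10 per 100 rate are all assumptions. They suggest fewer than one affected case by the serology route, but with few cases expected, one reclassification would show in the reported count and interval. It could also decide whether the threshold of more than 5 cases for plots is passed. The documents do not support reading this as a material bias in the primary rate or as a loss of cases. It is a definitional conflict that should be settled before the first data freeze.

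**What to change.** 1. In 2.7.2 and 3.5.5.3, define a breakthrough case for a type as a case in a subject who is PPE-eligible for that type, including seronegativity to both HPV 6 and 11 for HPV 6- or 11-related endpoints.
2. Amend PPE condition (3) to use the same sexual-activity period as the breakthrough rule, through dose 3, for both cases and person-time. Step 1 needs this. Defining breakthrough by PPE eligibility alone could otherwise turn a case in a subject who became active between Day 1 and dose 3 into a vaccine failure.
3. State that a case counts in the composite PPE analysis only if the subject is PPE-eligible for the type of that case.
4. Tabulate all remaining FAS cases separately by reason: seropositive to the type (or to either 6 or 11 for HPV 6/11 endpoints); series not completed within a year; sexual activity before the series was complete; other protocol violation.

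The cost is wording only. No new data are needed, because Section 3.2.2.6 already collects lifetime sexual history, including age at debut, once a subject reaches 16. The downside is that a few cases and a little person-time move between tables.

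### Cases with sexual activity before dose 3 are dropped from the primary effectiveness summary, but the per-protocol population tests naivety only at Day 1, so matching non-cases stay in the person-time (minor)

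*Combined protocol and SAP*

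**What the plan says.** Section 2.7.2 defines the primary group by dosing alone: "The primary analysis group will be those who have received 3 doses of 9-valent HPV L1 VLP vaccine within one year". It then makes two further conditions part of being a breakthrough case: the subject must have been "negative to the respective HPV type by serology prior to vaccination and were sexually naïve through the" third dose. The stated purpose is to "limit analysis of the prophylactic effect of the vaccine to subjects who were not infected prior to completion of the vaccination series".

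Section 3.5.5.3 repeats the case rule. A subject who meets an endpoint definition is not a breakthrough case if there is pre-vaccination seropositivity, or "evidence of sexual activity prior to the completion of their vaccination series), or who do not complete their three doses" within one year. It adds that "these cases will not be included in the primary summary of effectiveness endpoints"; they are summarized separately.

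Section 3.5.4.3 makes the PPE the primary population. Condition (1) is having "received 3 doses of 9-valent HPV L1 VLP vaccine within 1 year". Condition (2) is seronegativity to the relevant type at dose 1. Condition (3) is a general clause on protocol violations that could interfere with the evaluation, followed by: "Specifically, at base study Day 1, satisfied inclusion criterion 5". That criterion requires no coitarche yet and no plan to become sexually active from Day 1 through Month 7. The section explains that it was meant to capture subjects "therefore likely to be HPV-naïve during the period of vaccination with 9-valent HPV L1 VLP vaccine".

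**The concern.** The rule that removes a case is not the rule that removes a subject. Section 2.7.2 states its target in terms of subjects, not only cases. If the numerator follows that target and the denominator does not, the exclusion depends on outcome: a subject with early debut counts as follow-up while free of an endpoint and disappears from the count on reaching one. This can only lower the PPE rate, which favours the vaccine, and the exact Poisson interval of Section 3.5.5.3 does not reflect it.

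The other safeguards do not cover this window. Serology is taken at dose 1, so it cannot show an infection acquired between dose 1 and dose 3. Section 2.7.2 says that there are no PCR data before age 16. Sexual history is therefore the only information on that interval.

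**Working it through.** **1. The three grounds side by side.**

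| Ground | Applied to cases (2.7.2, 3.5.5.3) | Applied to all PPE subjects (3.5.4.3) |
|---|---|---|
| Three doses within one year | yes | yes, condition (1) |
| Seronegative to the type before vaccination | yes | yes, condition (2), type by type |
| Sexually naive | through dose 3 | condition (3) names status and stated plan at Day 1 |

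Only the third row differs. A plan stated on Day 1 is not observed behaviour, and no section expressly removes a non-case whose debut came after Day 1 and before dose 3.

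**2. Length of the window.** Section 3.2.2.1 places dose 3 at Month 6 ± 4 weeks, with 30-day months: 6 × 30 ± 28 = 152 to 208 days after Day 1. The one year in condition (1) is an outer bound.

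**3. Size.** The plan states no rate, case count or person-time, so there is no figure to reproduce. Let C be the cases in subjects naive through dose 3, T the PPE person-time, and f the share of T from subjects with debut between Day 1 and dose 3.

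- Literal rate = C / T
- Matched rate = C / ((1 − f) T)
- Literal / matched = 1 − f

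The documents do not give f; 1% to 5% is assumed. Illustration, also assumed: C = 10, T = 5000 person-years.

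| f | Matched person-years | Rate per 100 person-years |
|---|---|---|
| literal | 5000 | 0.200 (exact 95% CI 0.096 to 0.368) |
| 1% | 4950 | 0.202 |
| 2% | 4900 | 0.204 |
| 5% | 4750 | 0.211 |

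The interval runs from 0.48 to 1.84 times the estimate, so a shift of 1% to 5% is small beside it. With zero cases the estimate stays at 0 and only the upper limit moves: for an assumed 10,000 person-years and f = 2%, from 0.0369 to 0.0376 per 100.

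**4. f is a share of person-time, not of subjects.** If early-debut subjects are 2% of subjects but contribute twice the person-time each, f = 0.02 × 2 / (0.02 × 2 + 0.98) = 3.9%.

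**5. Debuts that cannot be dated.** Let h be the share of target person-time from subjects whose debut was after dose 3 but cannot be dated, with k times the rate of the others (both assumed). Excluding them all multiplies the rate by 1 / (1 + h(k − 1)). For h = 2% and k = 2 this is 1 / 1.02 = 0.980. With f = 2% as well, the matched 0.2041 becomes 0.2001, so a blanket exclusion would cancel the correction. This is a property of the remedy, not a defect of the plan, but it determines how the remedy should be written.

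**The case against.** The strongest reply is that a consistent reading exists. The three grounds in Section 3.5.5.3 match the three PPE conditions one to one, so that section may only restate PPE ineligibility for subjects who become cases. Condition (3) opens with a general violations clause that could take in debut before dose 3, and Section 3.5.1 has violations reviewed before each database freeze. Whether such a debut counted as a violation in the base study depends on the base protocol, which is not supplied. If it did, and if it was applied to everyone, the bias is zero. This reading is plausible and cannot be excluded. However, the text does not state it, the sentence that makes the clause specific points to Day 1, and Section 3.5 says that no separate SAP will be issued.

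Other parts of the reply stand. Section 2.7 is a summary that defers to Section 3.5, so its dose-only primary group is weak evidence by itself. Section 1.3 and Table 3-6 tie the Month 7 visit to dose 3. The horizon of criterion 5 may therefore run past dose 3 for every subject, although it still records a plan. The full analysis set applies no naivety rule to cases or person-time, and the excluded cases are reported separately. These make the dropped cases visible but do not correct the PPE rate. Finally, Section 3.2.2.6 collects age at debut, not a date. If that is recorded in whole years (the precision is not stated), it often cannot place debut on one side of dose 3.

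A reader might infer that the primary effectiveness rate is materially biased, or that the sponsor intends to filter cases only. The documents support neither: f is unknown, and intent is not stated.

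**Conclusion.** The conflict between the stated rules is real, but the point is minor. Read literally, the PPE rate is understated by the proportion f of person-time from subjects with debut between Day 1 and dose 3. That f is small is a judgement, because the documents neither give it nor bound it; f, h, k and the case counts above are all assumptions. For f of 1% to 5% the shift lies well inside the exact Poisson interval of the illustration. Effectiveness is for estimation only (Sections 2.1.3 and 3.5.2), so no test or decision rule is affected. The reason to act is that the primary rate now has two readings, one of which excludes by outcome, and a short wording change removes the ambiguity.

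**What to change.** - In PPE condition (3), state that evidence of sexual activity before dose 3 makes a subject PPE-ineligible whether or not the subject becomes a case. Base this on the sexual history already collected. Use one stated definition of sexual activity, because criterion 5 speaks of coitarche while Section 3.2.2.6 also counts oral sex and genital contact.
- Define a primary breakthrough case as an endpoint case in a subject who is PPE-eligible for that type, and align Sections 2.7.2 and 3.5.5.3 to this, including the description of the primary group.
- Treat debuts that cannot be dated against dose 3 identically in cases and non-cases, and report the rate with and without those subjects.
- Keep the full analysis set and the separate summary of excluded cases as planned.

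If the sponsor already means the general violations clause to cover debut before dose 3, saying so in condition (3) is enough to align the rule. The non-vaccine-type analysis uses the PPE conditions other than (2), so the change carries over to it.

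The cost is wording in three sections and one additional presentation of the rate. No new data collection is required, although recorded age at debut may leave some subjects undatable. The downside is a slight loss of PPE person-time and some misclassification from recalled age at debut. The rate is certain to move upward only for debuts that can be dated.
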